7.5 SECONDARY ENDPOINTS

- ODI
- VAS (Back and Leg)
- SF-12 Short Form Survey (Physical Function and Mental Health)
- Patient satisfaction survey

CONFIDENTIAL

[Diametros Medical, LB2CT]

Page **34** of **67**

• Neurologic status

7.6 RADIOGRAPHIC ASSESSMENTS

An independent radiographic core laboratory will be used to provide an unbiased assessment of all xrays and CT scans (pre-procedure through last follow-up assessment). All images will be evaluated in accordance with the Image Review Charter which is provided to the sites.

Radiographic evaluations include:

- Angular Range of Motion
- Translational Motion
- Device Condition
- Device Migration
- Device Dislodgement
- Bone-Implant Interface Changes
- Exuberant Bone Formation

Outside of this clinical investigation, in normal clinical practice, radiography or computed tomography is performed: before surgery, at the end of surgery, and as a follow-up at 6 months, 12 months, and 24 months. Consequently, the diagnostic activities at 6 weeks and 3 months are to be considered additional procedures to normal clinical practice and as such represent an increased risk. MRI scanners produce a strong magnetic field that attracts magnetic materials and can cause unwanted movement of the medical device. Radiofrequency energy and magnetic fields can cause heating of the implanted device and surrounding tissue. X-rays and CT scans expose the patient to radiation. Radiation exposure can accumulate over the patient's lifetime. The X-rays obtained during this study are more frequent than the number of X-rays participants would undergo as a standard of care for their medical condition. The patient will be given specific counseling about the risk of radiographic imaging during the consent process.

As discussed above, the diagnostic activities at 6 weeks and 3 months are to be considered additional procedures to normal clinical practice and as such represent an increased risk, however, these are essential procedures to meet the proposed objectives of this clinical investigation. All other diagnostic criteria in the clinical investigation are not considered burdensome and/or invasive.

8. SELECTION OF STUDY POPULATION

8.1 SUBJECT RECRUITMENT

Subjects participating in this study will be recruited from the investigators' standard patient populations. All patients presenting for treatment of lumbar spinal stenosis will be evaluated for study participation based on the inclusion/exclusion criteria listed below. Subjects must meet all of the following inclusion criteria and none of the exclusion criteria. The investigator maintains exclusive responsibility for the inclusion and exclusion of any potential study participant.

8.2 INCLUSION CRITERIA

In order to be eligible to participate in this study, subjects must meet all of the following criteria:

1. Male or female subjects \geq 45 years of age.

CONFIDENTIAL Page **35** of **67**

- 2. Persistent leg/buttock/groin pain, with or without back pain, that is relieved by flexion activities (example: sitting or bending over a shopping cart)
- 3. Subjects who have been symptomatic and undergoing conservative care treatment for at least 6 months.
- 4. Diagnosis of degenerative spinal stenosis of the lumbar spine, defined as the narrowing of the midline sagittal spinal canal (central) and/or narrowing between the facet superior articulating process (SAP), the posterior vertebral margin (lateral recess), and the nerve root canal (foraminal).
- 5. Radiographic confirmation of at least moderate spinal stenosis which narrows the central, lateral, or foraminal spinal canal at one or two contiguous levels from L1-L5. Moderate spinal stenosis is defined as 25% to 50% reduction in lateral/central foramen compared to the adjacent levels, with radiographic confirmation of any one of the following:
 - a. Evidence of thecal sac and/or cauda equina compression
 - b. Evidence of nerve root impingement (displacement or compression) by either osseous or non-osseous elements
 - c. Evidence of hypertrophic facets with canal encroachment

Note: All imaging studies used to confirm LSS are to be completed within 3 months prior to enrollment. Radiographic (imaging) confirmation of LSS on CT (or MRI if available in lieu of CT). In the case of a transitional L5/L6 segment with a sufficiently prominent L6 spinous process, these subjects may be included by a deviation request from the applicant.

- 6. Must present with moderately impaired Physical Function (PF) defined as a score of > 2.0 of the Zurich Claudication Questionnaire (ZCQ)
- 7. Must be able to sit for 50 minutes without pain and to walk 50 feet or more
- 8. Subjects who are able to give voluntary, written informed consent to participate in this clinical investigation and from whom consent has been obtained
- 9. Subjects, who, in the opinion of the Clinical Investigator, are able to understand this clinical investigation, cooperate with the investigational procedures and are willing to return for all the required post-treatment follow-ups.

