25% to 50% reduction in lateral/central foramen
compared to the adjacent levels, with radiographic
confirmation of any one of the following:
a) Evidence of thecal sac and/or cauda equina
compression.
b) Evidence of nerve root impingement
(displacement or compression) by either osseous
or non-osseous elements.
c) Evidence of hypertrophic facets with canal
encroachment.
Note: All imaging studies used to confirm LSS are to be
completed within 3 months prior to enrollment. Radiographic
(imaging) confirmation of LSS included MRI and/or CT. In
the case of a transitional L_{5/L_6} segment with a sufficiently
prominent L6 spinous process, these subjects may be included
by a deviation request from the applicant.
6. Must present with moderately impaired Physical
Function (PF) defined as a score of > 2.0 of the Zurich
Claudication Questionnaire (ZCQ).
7. Must be able to sit for 50 minutes without pain and to
walk 15 meters (50 feet) or more .
8. Subjects who are able to give voluntary, written
informed consent to participate in this clinical
investigation and from whom consent has been
obtained.
9. Subjects, who, in the opinion of the Clinical
Investigator, are able to understand this clinical
investigation, cooperate with the investigational

	procedures and are willing to return for all the required
	post-treatment follow-ups.
	Subjects who meet any of the following criteria will be excluded from participating in this study:

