	29. Involved in pending litigation of the spine or worker's compensation related to the back.
	30. Enrolled in the treatment phase of another drug or
	device clinical investigation (currently or within past 30 days).
	31. Congenital defect of the spine.
	32. Pregnant or lactating.
	33. Any further contraindications and limitations of the
	device as described in the instructions for use (IFU).
STUDV ENDPOINTS	
	Subjects will be evaluated at the 12 month follow up for the
	primary endpoint
	printing endpoints
	Efficacy success will be evaluated as a two-prong composite
Primary Endpoint	endpoint:
Lindey Endpoint	• ZCQ Responder (at least two of the three ZCQ
	domains)
	$\circ \ge 0.5$ point improvement in physical function. $\circ \ge 0.5$ point improvement in symptom severity
	• Mean satisfaction <2.5 points.

	 No secondary surgical intervention (SSI) including reoperations, revision, removals or supplemental fixation or clinical significant confounding treatments (i.e., epidural steroid injections at the index level, spinal cord stimulators or rhizotomies) through 12 months. Safety success will be evaluated using precision-based statistics to characterize the incidence of major device- or procedure-related complications, including: Device integrity failure (dislodgement, migration, or deformation). New or persistent worsened neurological deficit at the index level. Spinous process fractures. Deep infection, death, or other permanent device attributed disability. 		
Secondary Endpoints	 Oswestry Disability Index (ODI) Visual Analogue Scale (VAS) (Back and Leg) SF-12 Short Form Survey (Physical Function and Mental Health) Patient satisfaction survey Neurologic status 		
STATISTICAL CONSIDERATIONS			
Sample Size	Mimimum of 191 subjects- maximum of 250 subjects		
Primary Effectiveness Hypothesis	The primary effectiveness hypothesis is that the composite success rate for the Lobster device is larger than the performance goal of 61.1%.		
Compliance statement	This investigation will be conducted in compliance with the CIP, the current version of the Declaration of Helsinki, ISO14155, ICH-GCP (as far as applicable) as well as all national legal and regulatory requirements.		

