Moderate stenosis is diagnosed clinically through patient symptomatology and is confirmed through radiographic criteria. The clinical hallmark of moderate stenosis is persistent leg, buttock, or groin pain, with or without back pain, that is relieved by placing the spine in flexion (e.g., leaning forward or bending over a shopping cart). These patients are generally no longer responsive to varying non-surgical treatments to relieve pain. In order to assess the extent of the pain and impaired function, validated scoring systems such as the Zurich Claudication Questionnaire can be used. In the clinical trials supporting PMA approval of the X-STOP® and VertiFlex Superion devices, moderate stenosis was further defined, in part, as patients who present with moderately impaired Physical Function (PF) defined as a score of ≥ 2.0 on the Zurich Claudication Questionnaire. When stenosis reaches a moderate severity and non-surgical care no longer mitigates symptoms, the only way to achieve sufficient pain relief is through surgical means.

Confirmation of moderate spinal stenosis is obtained by radiographic measurements, often defined as 25% to 50% reduction in lateral and/or central foraminal area compared to the adjacent levels. In addition, the patient can exhibit other radiographic evidence of moderate stenosis, including cauda equina compression, nerve root impingement, and hypertrophic facets with canal encroachment.

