4.4 INDICATIONS FOR USE

The Lobster device is indicated as follows:

Lobster Implantable Dynamic Interspinous Device is indicated to treat skeletally mature patients suffering from pain, numbness, and/or cramping in the legs (neurogenic intermittent claudication) secondary to a diagnosis of moderate lumbar spinal stenosis, with or without Grade 1 spondylolisthesis, confirmed by X-ray, MRI and/or CT evidence by a thickened ligamentum flavum, narrowed lateral recess, and/or central canal or foraminal narrowing.

The Lobster device is indicated for those patients with impaired physical function who experience relief in flexion from symptoms of leg/buttock/groin pain, with or without back pain, who have undergone at least 6 months of non-operative treatment. The Lobster device may be implanted at one or two adjacent lumbar levels in patients in whom operative treatment is indicated at no more than two levels, from L1 to L5.

For this intended use, Moderate Degenerative Lumbar Spinal Stenosis is defined as follows:

- 25% to 50% reduction in the central canal and/or nerve root canal (subarticular, neuroforaminal) compared to the adjacent levels on radiographic studies, with radiographic confirmation of any one of the following:
 - Evidence of thecal sac and/or cauda equina compression
 - Evidence of nerve root impingement (displacement or compression) by either osseous or non-osseous elements
 - Evidence of hypertrophic facets with canal encroachment
- AND associated with the following clinical signs:
 - Presents with moderately impaired Physical Function (PF) defined as a score of 120 of the Zurich Claudication Questionnaire (ZCQ)

CONFIDENTIAL

[Diametros Medical, LB2CT] Pa

Page **29** of **67**

• Ability to sit for 50 minutes without pain and to walk 50 feet or more.

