7. STUDY DESIGN

Diametros is proposing a prospective multi-centre study with comparison to an SSED-based performance goal (PG). The proposed prospective clinical study will be actively and intentionally harmonized to previously cleared interspinous device studies, the Vertiflex Superion RCT (P140004). Prospectively defined evaluations of covariate balance and safety evaluations are included in the study design, supporting using a performance goal comparison for the primary endpoint. The proposed prospective clinical study is summarized in the table below. The inclusion/exclusion criteria, device indication, study population, study evaluations as well as follow-up intervals through 1-year are identical to that of the Superion RCT. This was done as part of the study design regime to promote and support the use of a Performance Goal comparison for the primary endpoint.

This clinical study is a prospective, multi-centered study using a historical control.

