19.2 PRIMARY ENDPOINT

Subjects will be evaluated at the 12-month follow-up for the primary endpoint.

Effectiveness success will be evaluated as a two-prong composite endpoint:

- ZCQ Responder (at least two of the three ZCQ domains)
 - $\circ \geq 0.5$ point improvement in physical function.
 - $\circ \geq 0.5$ point improvement in symptom severity
 - Mean satisfaction ≤ 2.5 points.
- No secondary surgical intervention (SSI) including re-operations, revision, removals or supplemental fixation or clinically significant confounding treatments (i.e., epidural steroid injections at the index level, spinal cord stimulators or rhizotomies) through 12 months.

The primary effectiveness hypothesis is that the composite success rate for the Lobster device is larger than the performance goal of 61.1%. A detailed description of the how the performance goal was calculated will be provided in the statistical analysis plan (SAP).

Formally, the hypotheses to be tested are:

H₀: The expected proportion of patients with composite success at Month 12 (p_T) is less than or equal to the performance goal (PG) of 61.1%.

CONFIDENTIAL Page **59** of **67** H_A: The expected proportion of patients with composite success at Month 12 (p_T) is greater than the performance goal (PG) of 61.1%.

These hypotheses may be symbolically represented as:

H_o:
$$p_T \le PG = 61.1\%$$

H_A: $p_T > PG = 61.1\%$

Where p_T is the composite success rate for subjects treated with the Lobster device.

A one-sided normal approximation binomial test with type 1 error set to α =0.05 will be used to demonstrate that the investigational device meets the performance goal.

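### Entry needs ZCQ physical function above 2.0, but the protocol reports 2.0 or above for the reference trials and still calls the criteria identical to support the performance goal

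*Protocol*

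**What the plan says.** Section 8.2, criterion 6: "Must present with moderately impaired Physical Function (PF) defined as a score of > 2.0 of the Zurich Claudication Questionnaire (ZCQ". The Study Summary agrees: "Function (PF) defined as a score of > 2.0 of the Zurich". Both are strict inequalities.

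Section 3.1, on the trials behind the X-STOP and Superion approvals: "moderate stenosis was further defined, in part, as patients who present with moderately impaired Physical Function (PF) defined as a score of ≥ 2.0". That is inclusive.

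Section 7 lists the inclusion/exclusion criteria, indication, population and evaluations, and ends the list with "follow-up intervals through 1-year are identical to that of the Superion RCT". Its next sentence gives the reason: to support a performance goal for the primary endpoint. Section 19.3 builds that goal from the pooled 71.1% success rate of the Superion study less 10 points, which is 61.1%.

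Section 4.4 places a physical function cut-off in the device indication too, but in the text at hand it is unreadable: "defined as a score of 120 of the Zurich Claudication Questionnaire (ZCQ". Section 4.3 says the study evaluates on-label use.

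A second ZCQ boundary also varies. The Study Summary has "Mean satisfaction <2.5 points" for the satisfaction domain, and Section 19.2 has "Mean satisfaction ≤ 2.5 points", as does Section 7.4.

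**The concern.** There is no concurrent control, so the 61.1% goal is only as good as the match between this population and the one that produced 71.1%. Section 7 offers identical entry criteria as a ground for that match, and on the protocol's own account they are not identical. A patient scoring exactly 2.0 could enter the reference trial as Section 3.1 describes it, and cannot enter this one.

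The mismatch falls on the instrument that defines success. A fall of at least 0.5 in physical function is one of the three responder domains. Lower scores are better: Section 3.3 calls a change from 3.2 to 1.3 an improvement. A baseline of 2.0 is the lowest score the reference rule admits, so it leaves the least distance to fall. If such subjects succeed less often, excluding them raises the Lobster rate relative to a goal derived with them included.

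**Working it through.** **The statements side by side**

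| Place | Physical function cut-off |
|---|---|
| Study Summary, criterion 6 | above 2.0 |
| Section 8.2, criterion 6 | above 2.0 |
| Section 3.1, reference trials | 2.0 or above |
| Section 4.4, indication | unreadable |
| Section 7 | entry criteria the same as the Superion RCT |

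The Study Summary and Section 8.2 agree with each other. If Section 3.1 is right about the Superion trial, Section 7 is wrong for this criterion. If Section 7 is right, either Section 3.1 or criterion 6 is wrong.

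**The plan's sample size reproduces**

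Inputs from Sections 19.2 and 19.3: p0 = 0.611, p1 = 0.711, one-sided α = 0.05, power 85%, 15% loss.

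n = [(1.645·√(0.611·0.389) + 1.036·√(0.711·0.289)) / 0.100]² = 161.73, so 162. Power at 162 is 85.1%. Allowing for loss, 162/0.85 = 190.6, so 191. Both figures match the protocol, and this point does not change them.

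**What the mismatch could do to the goal**

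Let f be the share of reference subjects scoring exactly 2.0 and r their success rate. The documents give neither, so both are assumptions. The reference rate among subjects above 2.0 is (0.711 − f·r)/(1 − f), and the like-for-like goal is that rate less 0.10. The last column is the chance that 162 subjects pass the test against 61.1% when the true rate p equals the like-for-like goal: Φ{[(p − 0.611)·√162 − 1.645·√(0.611·0.389)] / √(p(1 − p))}.

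| f | r | Reference rate above 2.0 | Like-for-like goal | Shift (points) | Chance of passing 61.1% |
|---|---|---|---|---|---|
| any | 71.1% | 71.1% | 61.1% | 0 | 5.0% |
| 1% | 50% | 0.706/0.99 = 71.3% | 61.3% | 0.2 | 5.6% |
| 5% | 60% | 0.681/0.95 = 71.7% | 61.7% | 0.6 | 6.7% |
| 5% | 50% | 0.686/0.95 = 72.2% | 62.2% | 1.1 | 8.7% |

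**The case against.** The strongest objection is that the symbol may simply have been misread. Section 4.4 shows that this very inequality was garbled at least once in the text copy. Against that, the strict form appears in two separate places, and in each list the inclusive sign in the age criterion (45 years or older) survives. The doubt justifies checking the source PDF; it does not dispose of the point.

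Section 7 also promises prospectively defined covariate-balance evaluations, and Section 19.2 leaves the derivation of the goal to the SAP. Neither makes the statement of identity true.

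Four stronger readings are tempting, and the documents do not support them:

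- A reader might infer that subjects at 2.0 could hardly respond. They have less room, not none, and two of three domains suffice, so symptom severity and satisfaction can carry them. The mean of 1.3 after treatment in Section 3.3 (overall ZCQ, not physical function) suggests that a fall from 2.0 to 1.5 is not out of reach. Subjects just above 2.0 have nearly the same room and remain eligible.
- A reader might put the bias as high as 3 points. That takes a 10% share and a 30-point deficit together (0.10 × 0.30), and neither has a source in the documents.
- A reader might conclude that criterion 6 should become 2.0 or above. The only basis is one background sentence in Section 3.1 about trials whose criteria are not in the document. The cut-off in the indication is unreadable, and a change could conflict with the on-label commitment in Section 4.3.
- A reader might treat the satisfaction boundary as an established conflict in the endpoint. The strict form stands only in the Study Summary table, whose text is badly corrupted, while Sections 7.4 and 19.2 agree on the inclusive form.

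**Conclusion.** The contradiction stands: the entry rule, the account of the reference trials and the claim of identical criteria cannot all be correct, and the primary comparison leans on that claim. The practical effect is confined to a score of exactly 2.0. Its likely direction favours Lobster, on the premise that subjects with the least room to improve succeed less often. It is probably small and cannot be sized from the documents: about 0.2 to 1.1 points on the goal if 1% to 5% of reference subjects scored 2.0 with 50% success, and nothing if their success equalled 71.1%. This is an inconsistency to be corrected, not evidence that the goal is invalid. Which cut-off is right cannot be decided from the protocol.

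**What to change.** Check the inequality signs in the source PDF. Then reconcile the physical function cut-off across the Study Summary and Sections 3.1, 4.4, 7 and 8.2, so that the entry rule agrees with both the indication and the reference trial's criterion. If the cut-offs really differ, withdraw the claim of identity for the entry criteria in Section 7 and state the difference there as a limit on the performance-goal comparison.

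As a secondary matter, if the source PDF also prints the strict satisfaction cut-off in the Study Summary, bring it into line with the inclusive one in Sections 7.4 and 19.2. Otherwise a subject scoring exactly 2.5 who meets only one other domain is a responder under one text and a failure under the other.

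The cost is a check of the PDF and an edit of a few symbols or one sentence. If the entry rule itself changes, that is a protocol amendment under Section 20.3 and alters who is eligible. The sample size stays at 162 evaluable and 191 enrolled.

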8.3 EXCLUSION CRITERIA

Subjects who meet any of the following criteria will be excluded from participating in this study:

- 1. Axial back pain only
- 2. Fixed motor deficit
- 3. Diagnosis of lumbar spinal stenosis which requires any direct neural decompression or surgical intervention other than those required to implant the control or investigational device
- 4. Unremitting pain in any spinal position
- 5. Significant peripheral neuropathy or acute denervation secondary to radiculopathy
- 6. Lumbar spinal stenosis at more than two levels determined pre-operatively to require surgical intervention
- 7. Significant instability of the lumbar spine as defined by \ge 3mm translation or \ge 5° angulation
- 8. Sustained pathologic fractures of the vertebrae or multiple fractures of the vertebrae and/or hips
- 9. Spondylolisthesis or degenerative spondylolisthesis greater than grade 1 (on a scale of 1-4)
- 10. Spondylolysis (pars fracture)

CONFIDENTIAL

- 11. Degenerative lumbar scoliosis with a Cobb angle of $> 10^{\circ}$ at treatment level
- 12. Osteopenia or osteoporosis. To confirm eligibility, at the Clinical Investigator's discretion, the following subjects may have a DEXA scan performed:
 - i. Women 65 or older
 - ii. Postmenopausal women < age 65
 - iii. Subjects with major risk factors for or diagnosed with osteoporosis or osteopenia
 - iv. If DEXA is required, exclusion is defined as a DEXA bone density measurement T score \leq -2.5
- 13. Morbid obesity, defined as Body Mass Index (BMI) greater than 40kg/m2
- 14. Insulin-dependent diabetes mellitus
- 15. Significant peripheral vascular disease (diminished dorsalis pedis or tibial pulses)
- 16. Prior surgery of the lumbar spine
- 17. Cauda equina syndrome (defined as neural compression causing neurogenic bowel or bladder dysfunction)
- 18. Infection in the disc or spine, past or present
- 19. Evidence of active (systemic or local) infection at time of surgery
- 20. Active systemic disease such as AIDS, HIV, hepatitis, etc.
- 21. Paget's disease at involved segment or metastasis to the vertebra, osteomalacia, or other metabolic bone disease
- 22. Currently undergoing immunosuppressive therapy or long-term steroid use
- 23. Known allergy to titanium or titanium alloys
- 24. Tumor in the spine or a malignant tumor except for basal cell carcinoma 25. Known or suspected history of alcohol and/or drug abuse
- 25. Prisoner or transient
- 26. Life expectancy less than two years
- 27. Angina, active rheumatoid arthritis, or any other systemic disease that would affect the subject's welfare or outcome of the clinical investigation
- 28. Any significant mental illness (e.g., major depression, schizophrenia, bipolar disorder, etc.) that could impair the consent process or ability to complete subject self-report questionnaires
- 29. Involved in pending litigation of the spine or worker's compensation related to the back
- 30. Enrolled in the treatment phase of another drug or device clinical investigation (currently or within past 30 days)
- 31. Congenital defect of the spine
- 32. Pregnant or lactating

